7.3.2. Missing Data Handling for Efficacy

Every effort will be made to minimize the number of dropouts and to document reasons for dropping out.

For FMMS score, the following imputation rules will be followed for missing data: For FMMS motor total score, If there are only 5 or less missing items, impute missing individual items at post-baseline visits using the Last-Observation-Carried-forward (LOCF) method; if more than 5 items are missing at a visit, then the total score will be set to missing. For UE-FMMS subscale score, If there are only 3 or less missing items, impute missing individual items at post-baseline visits using the Last-Observation-Carried-forward (LOCF) method; if more than 3 items are missing at a visit, then the UE-FMMS subscale score will be set to missing. For LE-FMMS subscale score, If there are only 2 or less missing items, impute missing individual items at post-baseline visits using the Last-Observation-Carried-forward (LOCF) method; if more than 2 items are missing at a visit, then the LE-FMMS subscale score will be set to missing.

For NeuroQOL with missing items, the raw score will be calculated using the rules that are specified in Section 9.2.4.

For efficacy analysis of the other secondary efficacy endpoints, missing response or scores will not be imputed. For questionnaire data excluding FMMS and NeuroQOL, when calculating the total score or any subscale scores with more than one item, if one or more 'related' items are missing at a visit, then the associated total or any subscale score will be set to missing.

7.4. POOLING OF CENTERS

Some surgical sites may not have sufficient number of subjects for the efficacy analyses. Such small surgical sites may be pooled by size within geographic region if necessary. The pooling of surgical sites will be finalized after enrollment is completed and before the database is locked. subject

All surgical sites with eleven or fewer subjects will be pooled by size within geographic region, with the intention that no pooled surgical site will contain more than 24 randomized subjects. In principle, surgical sites with 12 or more randomized subjects will not be pooled.

Within each geographic region, surgical sites with 11 or fewer subjects will be pooled, beginning with the surgical sites with the smallest number of subjects until the resulting pooled site has reached at least 12 subjects, and no more than 24 subjects. If the pooling cannot be performed within the geographic region, other sites in the close geographic region will be considered. The list of pooled sites for the present study based on the pooling strategy previously described is provided in following Table x.

INC1005439

Sponsor: San-Bio, Inc.

Protocol: SB-STR02

Final 1.0

Statistical Analysis Plan

Table 3 List of Pooled Sites

Pooled Site ID	Site ID ^(Number of Subjects, State)	Country	Number of Subjects
901	503 ^(5, GA) , 512 ^(2, AL) , 514 ^(2, FL) , 515 ^(5, SC)	USA	14
902	504 ^(2, MA) , 506 ^(2, IL) , 511 ^(8, PA) , 517 ^(1, NY)	USA	13
903	505 ^(7, CA) , 509 ^(5, TX)	USA	12
904	508 ^(7, KS) , 519 ^(9, KY)	USA	16

7.5. REPEAT OBSERVATIONS

For repeat observations of post baseline safety assessments (clinical laboratory, vital signs, ECG) in a scheduled visit, the last non-missing valid value for the visit and/or time point will be used in the analyses. All data regardless of whether it is collected at a scheduled or unscheduled visit will be listed.

Statistical Analysis Plan

8. DISPOSITION, DEMOGRAPHIC, BASELINE CHARACTERISTICS AND CONCOMITANT MEDICATION

8.1. SUBJECT DISPOSITION AND WITHDRAWALS

Subject disposition will be summarized. The number and percentage of subjects' screened, randomized, completed and early termination will be presented. Reasons for early termination from the study including adverse event, lost to follow-up, pregnancy, withdrawal of consent, protocol violation, physician decision, lack of efficacy, and other (specify) will be summarized by treatment group, combined SB623 2.5 and 5 million cells group, and overall.

Number and percent of subjects who received surgery will be summarized for each investigator site.

Subject completion status, date of study completion/early termination, and reason for early termination will be listed based on the information collected in the CRF. Other information collected at screening and information regarding emergency unblinding will be included in this listing as well.

The number and percentage of subjects discontinued by visit will be summarized by treatment group and overall.

Inclusion and exclusion eligibility will be listed separately.

8.2. DEMOGRAPHIC AND BASELINE CHARACTERISTICS

The following demographic and baseline characteristics will be summarized by treatment group and overall: subject's age, sex, race, ethnicity, weight, height, and Body Mass Index (BMI). Baseline characteristics including, but not limited to, number of strokes in the past, time from the last stroke, size of stroke, baseline FMMS motor total score, and baseline mRS score will be summarized. Below is a sample Statistical Analysis Software System (SAS[®]) reference code to calculate age:

```
age = floor((intck('month', BIRTHDT, RFSTDT) - (day(RFSTDT) < day(BIRTHDT))) / 12)
```

where RFSTDT is the informed consent date and BIRTHDT is the birth date. Age can be obtained directly from the SDTM dataset.

All demographic and baseline data will be presented in data listings.

8.3. MEDICAL HISTORY INCLUDING STROKE HISTORY

Medical history (including stroke history) will include significant medical conditions and surgical history, medications taken within 2 weeks prior to signing the Informed Consent

Statistical Analysis Plan

(IC). Medical history collected in the CRF will be coded to System Organ Class (SOC) and Preferred Term (PT) using Medical Dictionary for Regulatory Activities (MedDRA) (Version 18.0 or higher) and will be summarized by SOC and PT and sorted alphabetically. Subjects will be counted once if multiple histories are reported under the same level (SOC and/or PT) of summarization.

Medical history will be listed. Incomplete or missing date will be displayed as a dash for each letter or number, e.g. --MONYYYY or ----YYYY.

Stroke history will include date and cause of stroke, date confirmed if by CT or MRI, and location/size (volume in cc) of the affected brain region or changes occurring between signing of informed consent and study treatment administration.

A listing of stroke history will be provided.

8.4. PRIOR AND CONCOMITANT MEDICATION

Non-study treatment medications recorded in the CRF will be coded to Anatomical Therapeutic Chemical (ATC) levels and preferred name (PN) using World Health Organization Drug Dictionary (WHO-DD), June 2015 (Enhanced).

Investigational drugs or devices for any indication are not allowed during the study. All prior and concomitant medications including prescription and over-the-counter drugs taken during the 14 days prior to enrollment or used anytime during the study through 12 months post-Study Product (i.e., End of Study) or Early Termination will be documented. Documentation will include changes from the prior visit, start and stop dates, dose, and reasons for the medication use.

Prior medications are those which started prior to the day of surgery regardless of whether they were ended before the surgery date or not. Concomitant medications are defined as medications with a start date on or after the surgery date or medications with a start date prior to the surgery date and continued through post-surgery. Handling missing or incomplete start date in defining concomitant medications is described in Section 7.3.1.

A summary of prior and concomitant medications will be presented in tabular form by ATC level 3 (ATC3), PN and sorted alphabetically by ATC and PN. A subject will be counted only once within each level of summation if the subject has taken a medication more than once. A data listing will be provided for prior and concomitant medications.

Statistical Analysis Plan

9. EFFICACY

Descriptive summary statistics will be presented for actual measurement values and for changes from baseline by visit for the continuous variables. Number and percent of subjects will be summarized for each visit for the categorical variables.

Generalized Linear Mixed Model (GLMM) will be used for analysis of the primary endpoint FMMS response rate and the secondary endpoints mRS/ARAT/Gait Velocity/global ratings of perceived change response rate. Adjusted odds ratios and 95% confidence intervals (CIs) will be reported for the comparison of combined SB623 group versus sham control and separately for the comparisons of each SB623 group versus sham control.

Mixed Model for Repeated Measures (MMRM) analysis will be used to analyze continuous variables with more than one post-baseline assessment, whereas Analysis of Covariance (ANCOVA) will be used for continuous variables with one post-baseline assessment.

All efficacy analysis will be performed on the mITT population. The primary (FMMS response) and the key secondary endpoint (mRS) will be performed on the per protocol population as well. Details are given in Sections 9.1 and 9.2 below.

9.1. PRIMARY EFFICACY ENDPOINT AND ANALYSIS

9.1.1. FMMS Response - Primary Analysis

The primary analysis will be a comparison of SB623 combined groups (pooling both SB623 doses) to sham surgical control in proportion of subjects who achieve improvement of at least 10 points on the FMMS motor total score at Month 6 from Baseline.

The motor domain includes items measuring movement, coordination, and reflex action about the shoulder, elbow, forearm, wrist, hand, hip, knee, and ankle. For this study, only the components of the total motor scores corresponding to sum of the upper-and lower-extremity subscales are collected on the CRFs. The FMMS motor component consists of the 33-item upper-extremity subscale (UE-FMMS) and the 17-item lower-extremity subscale (LE-FMMS). Items are scored on a 3-point ordinal scale:

- 0 = cannot perform
- 1 = partial motion
- 2 = full motion

Individual items are then summed to determine scores for the two subscale scores, as well as a motor total score (calculated as summation of all item scores including the two subscales UE-FMMS and LE-FMMS). As a result, the UE-FMMS subscale score ranges from 0 to 66 and the LE-FMMS subscale score ranges from 0 to 34. The FMMS total motor score ranges from 0 (hemiplegia) to a maximum of 100 points (normal motor performance).

Statistical Analysis Plan

Hypothesis

Let $P_{SB623_combined\ doses}$ and $P_{sham\ control}$ represent the proportions of responders who have an improvement of at least 10 points on the FMMS motor total score at 6 months from Baseline in SB623 combined doses and sham control, respectively. The primary analysis will test the following hypothesis:

$H_0: P_{SB623_combined\ doses} = P_{sham\ control}$ versus the alternate $H_1: P_{SB623_combined\ doses} \neq P_{sham\ control}$

A GLMM model will be utilized using the mITT population as primary analysis. The GLMM model will have the outcome variable, FMMS responder (either \geq or $<$ 10 points improvement in FMMS), and independent variables of treatment, visit, treatment and visit interaction, and pooled surgical site as effects, and baseline FMMS motor total score and baseline mRS score as covariates. Treatment, visit, and pooled surgical site will be treated as categorical variables. Visit will be fitted as a repeated effect within subject. Link function will be set to logit and distribution to binary. An unstructured variance-covariance structure will be used. If this fails to converge then the following variance-covariance structures will be used based on the step-down order until model convergence is obtained: heterogeneous Toeplitz, heterogeneous autoregressive, heterogeneous compound symmetry, and then compound symmetry. The Kenward-Roger method will be used to estimate the denominator degrees of freedom. Adjusted odds ratios and 95% CIs for each visit will be presented for combined SB623 versus sham control. A separate analysis will be repeated for the comparisons of each SB623 group versus sham control for FMMS response. A forest plot of odds ratios and 95% CIs will be presented for individual/combined SB623 versus sham control. The results for Month 6 will be the primary interest.

For FMMS response, a supportive analysis will also be conducted based on the per protocol population using the same statistical method and following the same process for selection of variance-covariance structure.

A logistic regression analysis will be conducted by visit to include FMMS response as outcome variable, and independent variables of treatment and pooled surgical site as effects, and baseline FMMS motor total score and baseline mRS score as covariates. Odds ratios and 95% CIs will be reported for each visit.

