- 9 Diffusion tensor imaging (DTI) is an MRI technique which characterizes the magnitude, anisotropy and orientation of the diffusion tensor, using the pulsed-gradient, spin echo pulse sequence with a single-shot, echo planar imaging readout. DTI data will be obtained using whole brain coverage, a maximum of 2.5 mm isotropic resolution and at least 30 diffusion encoding directions and may be obtained using either a 1.5 or 3 Tesla MRI scanner. DTI is required for subjects at assessment sites with DTI capability. DTI is optional for sites without access to DTI-compatible scanners. Perfusion imaging is also required for subjects at assessments sites when the MRI has the capacity.
- 10 All efficacy assessments will be completed solely by blinded study personnel that do not have access to patient study safety information (this includes adverse events, concomitant medications, progress notes, and MRI reports).
- 11 The mRS Screening value is to be recorded by the clinical site utilizing the IXRS.
- 12 The subject global rating of perceived change should be completed by the subject. In the event the subject is not able to complete the questionnaire, the caregiver will be allowed to ask the questions of the subject and complete the questionnaire using the subject's answer(s).
- 13 Subjects will undergo study surgical procedure on Day 1 only after all other procedures for this visit have been completed.
- 14 Subjects will be discharged on Day 2 unless complications require a longer stay.
- 15 Adverse event collection begins from the time Informed Consent is provided.
- 16 During the surgical visit, adverse events and concomitant medications will be recorded pre- and post-surgery.
- 17 Including prior and concomitant medications at Screening.

Table 3: Schedule of Assessments (Continued)

Study Period	Follow-up	
Study Visit Type	Assessment	
Study Visit	9	10/ Early Termination
Study Day	252 (± 14)	336 (± 14)
Study Week	36	48
Study Month	9	12
Pregnancy Test ¹		X
Physical Exam		X
Physical Therapy Instruction and Subject Exercise Diary given to subject	X	
Subject Exercise Diary Review	X	X
Leg Activity Monitor Given to Subject	X	
Leg Activity Monitor Collected from Subject	X	X
Vital Signs	X	X
Chest X-Ray and ECG		X
Hematology	X	X
Serum Chemistry	X	X
INR		X
Serum for anti-HLA Antibodies ²		X
PBMC ²		X
Imaging--Head MRI ³		X
Imaging – Diffusion Tensor Imaging ⁴		X
Modified Rankin Score (mRS) ⁵	X	X
Fugl-Meyer Motor Score (FMMS) ⁵	X	X
Action Research Arm Test (ARAT) ⁵	X	X

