15.10 Clinical Stroke Evaluations

Detailed information regarding clinical stroke evaluations (including sample forms and instructions for conducting the evaluations) will be provided separately from this protocol.

Fugl-Meyer Motor Score (FMMS)

FMMS will be calculated as change from baseline for Months 1, 3, 6 (primary), 9 and 12. The treatment group will be compared to the control group based on the relative proportion of subjects who improve at least 10 points.

Modified Rankin Scale (mRS)

The mRS will be calculated to determine eligibility (mRS 2-4) at screening and again at Baseline, Months 1, 3, 6 (secondary), 9 and 12 months. The treatment group will be compared to the control group based on based on the relative proportion of subjects who improve at least

1 point. The mRS for all assessments except the Screening assessment will be recorded on video and reviewed in a blinded fashion by a central external rater.

Motricity Index

To ensure subjects have a defined motor deficit, an assessment of the subject's Motricity Index will be calculated at Screening for study eligibility purposes. Subjects will require either Motricity Index 30-75 (Upper Extremity Scale) OR 27-74 (Lower Extremity Scale).

Action Research Arm Test (ARAT)

ARAT scores will be calculated at Baseline and Months 1, 3, 6 (secondary), 9 and 12. The treatment group will be compared to the control group based on the relative proportion of subjects who improve at least 6 points.

Gait Velocity

Gait Velocity on a standard 10 m walk will be calculated at Baseline and Months 1, 3, 6 (secondary), 9 and 12. The treatment group will be compared to the control group based on the relative proportion of subjects who improve at least one functional level (e.g. from <0.4 m/s to 0.4-0.8 m/s or from 0.4-0.8 m/s to >0.8 m/s).

NeuroQOL

Two subdomains of the NeuroQOL will be assessed at Baseline and Months 1, 3, 6 (secondary), 9 and 12 using the Short Forms. The 2 subdomains include: Upper Extremity Function (Fine motor ADL) and Lower Extremity Function (Mobility). The treatment group will be compared to the control group based on the mean change in T Scores from baseline.

Global Rating of Perceived change from Baseline

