18.2.1.1 Primary Efficacy Analysis

The primary analysis will be a comparison of the proportion of SB623 treated subjects (pooling both SB623 doses) to sham surgical controls that achieve an improvement of at least 10 points on the Fugl-Meyer Motor Scale at 6 months from Baseline. A generalized linear mixed model (GLMM) will be utilized using the mITT population. The GLMM model will have the outcome variable, responder of FMMS (either \geq or <10 points improvement in FMMS at Month 6), and independent variables of treatment (SB623 combined doses vs. sham surgical control), FMMS baseline score and pooled surgical site as fixed effects.

Hypothesis

Let $P_{\text{SB623_combined doses}}$ and P_{Placebo} represent the proportions of responders who have an improvement of at least 10 points on the Fugl-Meyer Motor Scale at 6 months from Baseline in SB623 combined doses and placebo, respectively. The primary analysis will test the following hypothesis

$$H_0: P_{\text{SB623_combined doses}} = P_{\text{Placebo}} \text{ versus the alternate } H_1: P_{\text{SB623_combined doses}} \neq P_{\text{Placebo}}$$

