19.7 Computerized Systems Used for Source Data

A list of the computerized systems that will be used to create, modify, maintain, archive, retrieve, or transmit source data are presented below, pursuant to the Guidance for Industry Computerized Systems Used in Clinical Investigations, May 2007.

Table 5: Computerized Systems Used for Source Data

Protocol Step	Computerized System Type or Description
Informed Consent	A
Demographics	A
Inclusion/Exclusion Review	A
Eligibility Criteria Review	A
Randomization	C
Medical History (including stroke history)	A
Subject Exercise Diary	A
Leg Activity Monitor	D
Urine Pregnancy Test	A
Serum Pregnancy Test	B
Physical Examination	A
Vital Sign Measurements	A
Chest X-ray	A
12-lead ECG	D
Clinical Laboratory Evaluation (Hematology and Serum Chemistry)	B
INR	B
HLA Typing of each Subject	B
ApoE4 & BDNF Val66Met genotyping	B
Occult Malignancy	B
CESD-R Scale	A
Head CT	A
Imaging – Head MRI	D
Imaging – Diffusion Tensor Imaging	D
Modified Rankin Score	A
Motricity Index	A
Fugel-Meyer Motor Score	A
ARAT	A
Gait Velocity	A
NeuroQoL (2 subdomains)	A
Global Rating of Perceived Change (subject and clinician)	A
Adverse Events	A
Serum for anti-HLA Antibodies	B
PBMC Sample	B
Concomitant Medications	A
Sham Surgery or Cell Administration	A
Statistical Analysis	SAS [®] , version 9.4 or higher

A = EDC (Medidata RAVE); B = LIMS; C = IVRS; D = Core Laboratory Overread.

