3.6. TREATMENT ASSIGNMENT & BLINDING

This is a double-blind study. After study eligibility is confirmed, subjects will be randomized in a 1:1:1 ratio via an IXRS, stratified by Screening mRS score of 2, 3 and 4. Each subject will be randomized at a surgical site on the morning of the day of surgery (i.e. approximately 2-3 hours before surgery). The randomization will aim to be balanced, in terms of numbers of subjects between the treatment groups, within each surgical site.

Unblinded cell preparation staff will prepare and quality check the cell suspension for each subject per written procedures, randomization assignment, and other applicable local regulations as set forth in the protocol.

The neurosurgeon and or surgical staff will be unblinded. The sham surgery procedure will be scripted to mimic the cell administration procedure as closely as possible.

Subjects, investigator, staff, persons performing the assessments, sponsor, data analysts, and personnel at clinical and imaging core laboratories will remain blind to the identity of the treatment from the time of randomization until database lock and unblinding, using the following methods: randomization data are kept strictly

INC1005439

Sponsor: SanBio, Inc.

Protocol: SB-STR02

Final 1.0

Statistical Analysis Plan

confidential until the time of unblinding, and will not be accessible by anyone else involved in the study. MRIs will be over-read by a central reader post-surgery and blinded imaging reports will be sent to the assessment site staff.

The following are the exceptions to those staff required to remain blinded: DSMB members, including the unblinded statistician and programmers from the statistical service provider, individuals involved in regular review of safety data, clinical data, imaging service provider, unblinded cell preparation staff, unblinded neurosurgeon and OR surgical staff, and unblinded study monitor.

The blinded treatment assignment/dose information is to be broken only in an emergency when knowledge of such treatment may have an impact on further treatment decisions or aid in the emergency treatment of the subject. The Investigator will obtain the treatment assignment for the specified subject by accessing the IXRS. Date and reason for unblinding are to be promptly communicated via telephone and in writing to the Medical Monitor and documented in the CRF.

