7.2. KEY DEFINITIONS

7.2.1. Baseline

Baseline is defined as the last measurement before surgery.

Statistical Analysis Plan

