APPENDIX I SAMPLE SAS CODE IN STATISTICAL ANALYSIS

- 1) Binary endpoint by generalized linear mixed model:

```
proc glimmix data=dataset order=data;
class treatment visit subjid pooled_site;
model response(event='1')= treatment visit treatment *visit baseline pooled_site/ dist=binary
link=logit ddfm=KR OR;
random visit/subject=subjid residual type=xx;
lsmeans treatment*visit/pdiff cl;
run;
```

- 2) Linear mixed model for repeated measures:

```
proc mixed data=dataset;
class treatment visit subjid pooled_site;
model chg=treatment visit treatment*visit baseline pooled_site /ddfm=KR;
repeated visit/subject=subjid type=xx;
lsmeans treatment*visit/pdiff cl;
run;
```

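### Should the primary model use the Screening mRS stratum, and say whose mRS rating counts, rather than adjust for Baseline mRS?

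*SAP*

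**What the plan says.** **Randomisation.** SAP 3.6 has subjects "stratified by Screening mRS score of 2, 3 and 4". Footnote 11 to the schedule in Protocol 9.1 gives the source: "The mRS Screening value is to be recorded by the clinical site utilizing the IXRS".

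**Primary model.** SAP 9.1.1 fits treatment, visit, their interaction and pooled surgical site, with "baseline FMMS motor total score and baseline mRS score as covariates. Treatment, visit, and pooled surgical site will be treated as categorical variables". SAP 7.2.1 sets the time point: "Baseline is defined as the last measurement before surgery". The schedule has mRS rated at Screening and again at Visit 2, so Baseline is normally Visit 2.

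**Other statements of the model.** Protocol 18.2.1.1 lists treatment, "FMMS baseline score and pooled surgical site as fixed effects", with no mRS term. The binary-endpoint code in SAP Appendix I has "treatment visit treatment *visit baseline pooled_site/ dist=binary", a single unnamed baseline term.

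**Who rates mRS.** Protocol 15.10 says that every mRS except Screening "will be recorded on video and reviewed in a blinded fashion by a central external rater". Table 5 in Protocol 19.7 codes mRS as A, under the key "A = EDC (Medidata RAVE); B = LIMS; C = IVRS; D = Core Laboratory Overread". The SAP does not mention a central mRS rater.

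**The concern.** An analysis is normally expected to reflect the restriction used in randomisation. Here the stratifying rating and the adjusting rating are two separate assessments. They can be 82 days apart under the protocol windows (Day -84 to Day -2) and 19 days apart under the SAP's (Day -21 to Day -2). The SAP does not say that one stands in for the other. If the stratum predicts response and the model misses it, the treatment test can lose some power or drift from its nominal size.

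Two further points make it look worse. The primary model appears in three places, and only one has an mRS term, so a reader might think the choice of covariate was still open. And if the central review yields its own score, two mRS values could exist per visit. The SAP would then not say which one enters the covariate or defines the 1-point mRS response, which SAP section 9 calls the key secondary endpoint.

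**Working it through.** **1. Is Baseline mRS a legitimate covariate?** Visit 2 falls on Day -21 to -2. SAP 3.6 places randomisation on the morning of surgery, and no mRS is scheduled between the two. The rating therefore precedes allocation and cannot be affected by it. If Visit 2 were missed, the definition in SAP 7.2.1 would fall back on Screening. The form of the term can also be read from the text: mRS is called a covariate and is left out of the list of categorical terms, so it enters as a number.

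**2. The plan's own sample size.** With 11.7% against 33%, 2:1 allocation, two-sided 0.05 and 80% power, the pooled rate is (0.117 + 2 × 0.33)/3 = 0.259. Sham n = [1.960 × √(0.259 × 0.741 × 1.5) + 0.842 × √(0.117 × 0.883 + 0.33 × 0.67/2)]² / 0.213² = (1.052 + 0.389)² / 0.0454 = 45.8, so 46 sham and 92 treated, 138 in all, as stated. The formula contains no covariate or stratum, so the choice of mRS rating does not affect it.

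**3. Does the choice of rating matter?** Inputs from the documents: N = 138, 2:1 allocation in blocks within Screening mRS, and the two response rates above. Assumed: mRS shares of 25/45/30%, Screening-Baseline agreement of 60 to 100%, and a log-odds of response per Baseline mRS point of 0 or -0.7. In the earlier study, Protocol 3.3 reports 2 of 18 improved and 1 worsened, so 15/18 = 83% were unchanged. Each cell has 3,000 trials with a logistic Wald test at one time point. Entries are the percentage of trials rejecting with no mRS term / Baseline mRS / Screening stratum.

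| Agreement | Log-odds per point | Null | True effect |
|---|---|---|---|
| 60% | 0 | 3.3 / 3.3 / 3.5 | 79.3 / 79.6 / 79.8 |
| 60% | -0.7 | 3.6 / 3.4 / 3.8 | 79.8 / 81.5 / 80.9 |
| 75% | 0 | 3.6 / 3.7 / 3.7 | 79.3 / 79.5 / 79.9 |
| 75% | -0.7 | 3.2 / 3.4 / 3.6 | 78.7 / 81.1 / 80.3 |
| 90% | 0 | 3.2 / 3.4 / 3.4 | 80.0 / 80.2 / 80.6 |
| 90% | -0.7 | 3.4 / 3.4 / 3.8 | 78.6 / 79.9 / 80.0 |
| 100% | 0 | 3.3 / 3.3 / 3.4 | 79.5 / 79.8 / 80.1 |
| 100% | -0.7 | 2.7 / 2.9 / 3.0 | 80.4 / 82.3 / 82.6 |

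Baseline and Screening differ by at most 0.4 points under the null and 0.8 points in power. The simulation standard error of a single entry is about √(0.035 × 0.965/3000) = 0.3 points under the null and √(0.8 × 0.2/3000) = 0.7 points for power. Including Baseline mRS rather than no mRS term gains 0.2 to 2.4 points of power.

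A second set added baseline FMMS and 11 site levels, with 12,000 trials per scenario and response driven by Screening mRS, Baseline mRS or neither. Null rejection was 4.4 to 5.3% with Baseline mRS and 4.7 to 5.5% with the stratum. With each test set to 5%, using the stratum instead changed power by -1.0 to +0.5 points.

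**4. Whose score?** Protocol 11.0 item 3c assigns efficacy assessments solely to the assessors at assessment sites. Table 5 gives mRS the EDC code, whereas MRI, ECG and the leg monitor carry the core-laboratory code. Protocol 15.10 says that the videos are reviewed. It does not say that the review produces a second score or replaces the site's, and it leaves instructions to separate materials.

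**5. Three statements of the model.** Protocol 18.2 hands the details of method to the SAP. Protocol 18.8 requires departures from the protocol analysis to be explained in the final report. Appendix I is labelled as sample code, covers binary endpoints in general and uses placeholders such as `dataset` and `type=xx`. Its single baseline term is exactly right for the mRS response model in SAP 9.2.1, whose only covariate is baseline mRS.

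**The case for a change.** The strongest counter-argument is about the score source. A 1-point threshold on an ordinal scale is sensitive to who does the rating. Suppose a separate central score exists, and site and central readings agree with probability q, otherwise differing by +1 or -1 equally, independently at each visit. With h = (1-q)/2 and d = (1-q²-2h²)/2, and true change as in the earlier study, responder status differs by source in (17/18)d + (1/18)h² of subjects. For q = 0.80, 0.90 and 0.95 that is about 16, 9 and 5%.

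The arithmetic is right, but it rests on three assumptions: a second score that the documents do not establish, agreement rates that they do not give, and errors that are independent between Baseline and Month 6. An assessor who consistently rates a subject high or low cancels out of the change. If the error carries over with probability c, the share scales by (1-c): about 8, 4 and 2% at c = 0.5, and zero at c = 1. What stands is that the SAP could have said in a sentence what the video review is for.

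It is also true that models with and without the mRS term fell on opposite sides of 0.05 in 1.1 to 4.3% of simulated trials with a true effect, and in 0.6 to 1.7% under the null. That would matter if the choice were open until the data were seen. The finalised SAP text names the covariate, so the choice is already made.

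Finally, a Baseline rating might fall outside 2 to 4, which the mRS subgroups in SAP 9.3 do not anticipate. A numeric covariate takes such a value without difficulty, and SAP 9.3 combines subgroups of fewer than 10.

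**Conclusion.** No change follows. The primary model adjusts for a valid pre-randomisation covariate whose time point is fixed and whose numeric form can be read from the text. Replacing it with the Screening stratum would move size-equalised power by -1.0 to +0.5 points, which gives no reason to prefer it. Nor should the SAP be made to say that Baseline mRS represents the stratum. No section gives that purpose, and the same covariate appears in the ARAT, gait, NeuroQOL and global-rating models, which fits a plain prognostic role just as well.

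The remaining items are editorial: the sample code shows one covariate where 9.1.1 has two, SAP section 12 does not list the added mRS term, and the SAP is silent on the central review. An analyst would follow the SAP text over the template, use the EDC score, and report the departure under Protocol 18.8.

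The sizes rest on assumed mRS shares, agreement rates and prognostic strength. They come from single-time-point logistic tests, not the repeated-visit GLMM. The reading on score source rests on Protocol 11.0 and Table 5, since the separate rating instructions are not available.
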